5.4 Treatment Assignment Procedures

5.4.1 Randomization Procedures

Eighteen practices (comprising the clusters) will be included in the study. Practices will be randomized to one of the two arms using a restricted randomization scheme with the constraint that 9 practices will be assigned to each arm. This approach will involve the computation of a balance score (for each candidate randomization) based on marginal differences in three key

practice-level variables: % Medicaid-enrolled patients [20% to 40% and >40%], ratio of patients to providers, county [Cuyahoga vs. other]). We use the first generated (constrained) randomization that provides good balance according to a pre-selected balance criterion; it may be reasonable to require perfect marginal balance, if (as we expect) there are a reasonably large number of randomizations that yield this.

5.4.2 Masking Procedures

Parent/caregiver participants will be blinded to the intervention arms of the main trial. Furthermore, parent/caregiver participants will not be aware of what is involved in the study procedures being followed at other clinics. Study staff conducting dental screenings will also be blinded.

5.5 Subject Withdrawal

5.5.1 Reasons for Withdrawal

Participants are free to withdraw from participation in the study at any time upon request, as outlined in the consent form documents.

Participants who drop out (or withdraw) from the study by their own choice will be considered dropouts/withdrawals. Participants who are discontinued from the study by one of the study personnel will be also be considered a dropout/withdrawal.

An investigator may terminate a study subject's participation in the study if:

- Any medical condition or situation occurs such that continued participation in the study would not be in the best interest of the participant.
- The subject meets an exclusion criterion (either newly developed or not previously recognized) that precludes further study participation.

5.5.2 Handling of Subject Withdrawals or Subject Discontinuation of Study Intervention

All reasons for dropout/withdrawal or discontinuation of the study intervention will be documented in the tracking database and reviewed by the study team and reported to the NIDCR Medical Monitor and DSMB. For gathering information on discontinuation, study staff will be contacting subjects at several time points. Study staff will contact parent/caregivers within 2 weeks of WCVs #1 and #2 to collect B1 questionnaires not previously returned, 6 months after WCVs #1 and #2 to complete B2 questionnaires, and 3 months and 2 weeks before WCVs #2 and #3 to remind caregivers to schedule/attend WCV.

In the event of a subject telling study staff that he/she is dropping out of the study, the study staff should gather the following information as much as the participant allows.

- Record the reason for dropping out of the study.
- Record any adverse event reported by the subject.

- Complete the appropriate questionnaire nearest the drop out time point.

If it is determined by study staff that a participant should be discontinued from the study, the decision to withdraw a participant must be discussed and confirmed by the PI.

Caregiver/child dyads that withdraw during the baseline (T_0) data collection window will be replaced by recruitment of additional parent/child dyads to reach enrollment goals.

Caregiver/child dyads that withdraw or that are lost to follow-up any time after the baseline data collection window will not be replaced, but data collected up to the point of withdrawal will be used for analysis.

Providers that withdraw after receiving the study intervention will not be replaced. See Section 7.1.4.

5.6 Premature Termination or Suspension of Study

This study may be suspended or prematurely terminated if there is sufficient reasonable cause. Written notification, documenting the reason for study suspension or termination, will be provided by the suspending or terminating party to the Principal Investigator (PI), Medical Monitor/DSMB, or NIDCR. If the study is prematurely terminated or suspended, the principal investigator will promptly inform the IRB and will provide the reason(s) for the termination or suspension.

Circumstances that may warrant termination include, but are not limited to:

- Determination of unexpected, significant, or unacceptable risk to subjects.
- Insufficient adherence to protocol requirements.
- Data that are not sufficiently complete and/or evaluable.
- Determination of futility.

6 STUDY INTERVENTION

Refer to **Appendix B** for more details on section 6 in the Fidelity Monitoring Plan.

6.1 Study Behavioral or Social Intervention(s) Description

Complete descriptions of the interventions are given in the fidelity monitoring plan (Appendix B).

The interventions for this study are on two levels as follows: *Provider*: Common-Sense Model of Self-Regulation (CSM) based education and skills training for the pediatrician/nurse practitioner to understand chronicity of caries, and communicate the core OH facts to the parent, provide a prescription to take the child to the dentist together with a list of area dentists accepting Medicaid, and document OH in EMR. *Practice*: enhancements to the EMR system to include OH status will be implemented prior to enrolling any parent into the study. This will promote adoption of systematic EMR documentation of OH status that can facilitate follow-up with parent at subsequent WCVs.

Table 6.1.1: Theoretical perspectives for behavioral interventions at each level

Socio-ecological levels	Change objectives	Theoretical methods (theory)	Practical application and delivery of interventions
Individual (parent/caregiver)	
 Learn chronicity of caries and seriousness regarding primary teeth Behavioral capability / awareness for seeking dental care Skills & self-efficacy for taking child to dentist 	
 Information processing and transfer (CSM) Self-management (CSM, SCT) Active learning with images (CSM, SCT) Reinforcement (SCT) 	
 OH assessment and facts from primary care doctors Educational materials with illustrations List of dentists
Interpersonal (provider)	
 Behavioral capability / knowledge of core OH facts Skills & self-efficacy to communicate core OH facts Refer to dentist for dental care 	
 Information processing and transfer (CSM) Active learning (SCT) Persuasion (communication) Reinforcement (SCT) 	
 Brief lectures through seminars, lunch and learn, webinars etc. Skills and communication training to impart one-on-one OH facts to parent/caregivers Referral to dentist together with list of Medicaid accepting dentists
Organization (practice)	
 Awareness of OH in practices Integrate OH assessment in EMR Systematically document OH for quality improvement and monitoring 	
 Information transfer (CSM) Identifying practice attributes and champion/s (Diffusion of Innovation theory) Active learning (SCT) Feedback (SCT) Creating OH protocols (SCT) 	
 EMR enhancement and prompts for OH documentation Skills training of practice providers and staff to document Standardized OH protocols Newsletters to communicate progress in practices

CSM – Common Sense Model of Self-Regulation, SCT – Social Cognitive Theory

6.2 Administration of Intervention

Arm A

The provider-level intervention consists of CSM theory based didactic education and skills training for providers to learn about the chronicity of caries, to communicate core oral health facts to parent/caregivers at the well-child visit (WCV), to provide a prescription to take their child to the dentist together with a list of area Medicaid-accepting dentists, and to document OH in EMR. By enhancing dental knowledge and skills of the pediatric providers through the CSMbased education, interactive practice sessions with standardized patients, and training in

EMR documentation, parents/caregivers will receive the core OH facts along with coping and action supports (e.g., prescription to dentist, list of Medicaid accepting dental providers) from the child's provider. Providers will receive didactic education with pre- and post-tests and interactive skills training with standardized patients (SPs). Providers will also be given materials (Appendix D) to help them implement the intervention including: training manual that includes a didactic section on oral health and skills section on communication (more specifics on the training manual will be detailed in the MOP), pocket card (with core oral health facts listed), and flip chart (to use during oral health communication to caregivers). The training will be delivered to providers in two 45-minute sessions (didactic education first and then skills training) at their individual practice prior to study enrollment of caregiver and child participants at WCV #1. There will be a booster education session before WCV #2. The final WCV #3 will serve as the maintenance visit.

Arm A will also have practice-level intervention that includes incorporation of four oral health questions into the practice EMR. As a result of this practice-level intervention, Arm A providers will receive EMR training to document the oral health encounter. The EMR training will occur simultaneously with the didactic and skills training sessions prior to WCV #1 and the booster session before WCV #2. Providers will receive an EMR training manual for documentation (more specifics on the EMR training manual will be detailed in the MOP; see Appendix D for EMR screenshots). While the majority of University Hospitals based practices have oral health questions incorporated in their EMR, the OH questions are hidden and will be available only to providers with appropriate training in practices in study Arm A. The other non-UH based practices randomized to study Arm A will have the OH questions incorporated prior to enrollment of caregiver and child participants.

Parents/caregivers of the providers and practices in Arm A are the recipients of the provider and practice level interventions. Parent/caregivers will receive CSM-based oral health facts, prescription to go to the dentist together with a list of Medicaid-accepting dentist.

Arm B

Providers will receive the standard AAP based didactic education in a 45-minute session prior to WCV #1 and a booster session prior to WCV #2. Arm B providers will not receive any CSMbased education, skills training or the practice-level intervention.

Parents/caregivers in this arm will receive the usual care for oral health as followed by the providers and practices currently.

6.3 Procedures for Training Interventionists and Monitoring Intervention Fidelity

Refer to **Appendix B** for the Fidelity Monitoring Plan for the study.

All study staff will receive Human Subject Protection, Good Clinical Practice (GCP), protocol, and MOP training.

6.3.1 Procedures for Training Interventionists

Provider training (Arm A) will be conducted by experts on the curriculum team: Drs. [name] (who has more than 20 years of experience as an oral health researcher), [name] (who has spent more than 20 years teaching residents as chief of pediatric dentistry), and [name] (a communication specialist with more than 10 years of teaching experience in the area of primary care delivery). The provider will need to complete three components satisfactorily to be considered as trained: (1) didactic training (assessed through pre and post test); (2) skills training (assessed through standardized communication checklist, and self-efficacy pre and post test); (3) observation of the first OH encounter of the provider by study staff (assessed through the standardized communication checklist). A score card will be given that outlines the established target goals which are elaborated in detail in the Fidelity Monitoring Plan in Appendix B).

Training materials, including scripts and narrated slides, will ensure that the curricula are delivered in the same way for each group of clinicians to ensure fidelity of the training delivery. A training manual (for Arm A) more specifics will be detailed in the MOP), EMR training (only Arm A) and flip chart and pocket card (Arm A) have been developed to provide information as needed (Appendix D, also includes EMR screen shot). Additional booster training for providers will be conducted, if necessary, to address deviations in protocol.

6.3.2 Procedures for Monitoring Intervention Fidelity

Arm A

Providers' implementation of the provider-level intervention will be assessed at all 3 WCVs. Two - three of each provider's OH encounters with parent/caregiver will be observed or audiotaped and then evaluated by the study staff using a standardized communication skills checklist (Appendix E) at WCV #1 and WCV#2. The results of the observation/audiotaping will be given to the provider as a scorecard to provide feedback regarding whether the provider met the established target goals which are elaborated in detail in the Fidelity Monitoring Plan (Appendix B). All enrolled caregivers will complete an exit questionnaire (Appendix E) after the OH encounter to assess whether the provider communicated the OH facts and gave them the prescription and list of dentists. So, *Provider-level fidelity measures* to assess whether providers communicated the core OH facts to caregivers and delivered the prescription to go to the dentist and list of area Medicaid-accepting dentists include: 1) standardized communication skills checklist completed by study staff and 2) parent exit questionnaire (Appendix E).

Providers' implementation of the practice-level intervention will be assessed at all 3 WCVs. Study staff will complete monthly EMR audits (at all 3 WCVs) of all enrolled patients' EMR chart to assess whether providers' OH documentation was complete.

The *practice-level fidelity measure* to assess adoption of the intervention is the EMR Audit of Practice form completed by study staff (Appendix E).

Arm B

Since Arm B does not receive the interventions, monitoring procedures outlined below will be used to monitor baseline rate and check for contaminations between study arms.

Two - three of each provider's OH encounters will be randomly selected for observation/audiotaping and evaluation by study staff using the same standardized communication skills checklist used in Arm A. Scorecards will not be given to Arm B providers, but evaluation with the checklist will serve to document the communication of OH facts due to enhanced usual care.

Study staff will complete monthly EMR audits using the EMR Audits of Practice form (at all 3 WCVs) for 20% of enrolled patients' EMR chart to assess whether any oral health documentation was completed despite not receiving EMR training. (Appendix E).

6.4 Assessment of Provider Compliance with Study Intervention

Arm A

Compliance with the provider-level intervention: The study staff's direct observation/audiotape of provider encounters will provide an assessment of whether providers communicated all 6 core OH facts and gave caregivers the prescription to go to the dentist along with list of area Medicaid-accepting dentists. It will also be used to assess whether the provider initiated the topic of the child's dental care with the caregiver and used appropriate communication skills. The exit questionnaire completed by parent/caregivers will assess whether their pediatrician/nurse practitioner communicated OH facts and gave them the prescription to go to the dentist and list of dentists (i.e. whether the caregiver received and understood the main points of the provider's oral health communication and the prescription they were being given). Compliance will also be verified with the numbered prescriptions and list of dentists to determine the total number given to each provider's enrolled caregivers.

Compliance with the practice-level intervention: The study staff will conduct EMR audits of all enrolled patients to determine whether the OH documentation was complete, i.e. provider documented whether or not they did the following during the OH encounter: 1) examined child's teeth for white or brown spots, 2) asked whether child had a dental visit in the past 12 months, 3) communicated core OH facts, and 4) gave caregiver a prescription to take their child to the dentist along with a list of Medicaid-accepting dentists in the area.

Arm B

Compliance with the provider-level intervention: Study staff evaluation of providers' OH encounters and parent exit questionnaires completed by a random 20% selection of each provider's enrolled patients will be used to assess whether Arm B providers communicated OH facts to identify possible contamination bias in delivery of the provider-level intervention (i.e. provider is giving caregivers provider-level intervention materials not associated with their assigned arm).

Study staff will perform EMR audits on a random 20% selection of each provider's enrolled patients to identify possible contamination bias in delivery of the practice-level intervention (i.e. providers are documenting patients' OH without having received the practice-level intervention).

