7.2 Parent/Caregiver and Child

7.2.1 Baseline Visit: WCV #1

At WCV #1 (T₀: Day 0)

Before Provider Encounter

- Study Staff will recruit 1024 parent/caregivers and their children from the 18 practices (approximately 56-57 participants/practice) using an in-person approach. Parents/caregivers attending well-child visits with 3-6 year old children will be approached for participation.

- In the waiting area/exam room of the pediatric practice, study staff will review inclusion/exclusion criteria as outlined on the screening survey to determine parent/caregiver and child eligibility (Refer to Sections 5.1, 5.2).
- Review the written consent form with the potential participant; study staff signs the consent form acknowledging that informed consent was reviewed and caregiver signs acknowledging consent was obtained (Appendix C: Consent forms).
- In the waiting area/exam room of the pediatric practice, study staff will obtain contact information.
- In the exam room, caregivers will complete the following self-administered Baseline questionnaires: A1: Illness Perception Questionnaire-Revised for Dental (IPQ-RD) and A2: Parent Questionnaire (Appendix E: Questionnaires & forms).
- In the exam room, dental hygienist will perform child dental screening examination and study staff will record results of the dental screening examination. Results will not be available to the provider, unless the hygienist finds that the child has urgent needs that require immediate attention. (Appendix E: Questionnaires & forms).

During Provider Encounter in the Exam Room

- Caregivers attending WCV's will receive OH information, prescription to take the child to the dentist + list of local Medicaid-accepting dentists from provider, based on study arm.
- Caregivers attending WCV's may have study staff audiotape or directly observe the provider encounter to evaluate provider's delivery of OH communication (for a sample of visits).

After Provider Encounter in the Exam Room/Waiting Area

- Caregivers will provide feedback about the OH information given to them during the medical visit with a short self-administered exit questionnaire (A3: [Appendix E: Questionnaires & forms]).
- Caregivers will be given the B1: Follow-up IPQ-RD (Appendix E: Questionnaires & forms) to be completed and returned (in postage paid envelope or in person, based on participant preference).

After WCV #1 (T₁)

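### Section 6.4 checks Arm B contamination on a random 20% of exit questionnaires, although the visit schedule collects them with no restriction by arm

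*Combined protocol and SAP*

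**What the plan says.** **Exit questionnaires.** Under Arm A, section 6.3.2 has all enrolled caregivers complete the exit questionnaire. Under Arm B, section 6.4 says that "parent exit questionnaires completed by a random 20% selection of each provider's enrolled patients will be used to assess whether Arm B providers" communicated oral health facts, so as to detect delivery of Arm A content. The visit schedule makes no such distinction. For WCV #1, section 7.2.1 says: "Caregivers will provide feedback about the OH information given to them during the medical visit with a short self-administered exit questionnaire". Sections 7.2.2 and 7.2.3 repeat this for WCV #2 and WCV #3, and section 8.1.3 lists A3 at T0, T3 and T6. None of these is limited by arm or to a sample.

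**Observed encounters.** For Arm A, section 6.3.2 says: "Two - three of each provider's OH encounters with parent/caregiver will be observed or audiotaped". For Arm B it says: "Two - three of each provider's OH encounters will be randomly selected for observation/audiotaping". The number per provider and the checklist are the same; a selection rule is given only for Arm B. Section 6.3.1 also makes "observation of the first OH encounter of the provider by study staff" a condition for an Arm A provider to count as trained, scored on the communication checklist.

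**Purpose.** Section 6.3.2 gives Arm B monitoring two aims: to record the baseline rate and to check for contamination between arms. The protocol sets no sample size or precision target for either. Fuller fidelity detail is referred to Appendix B, which is not in the text available for this review.

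**The concern.** How far the arms differed in what families received determines how a null result is read: the bundle may not work, or the arms may have been too alike. Fidelity and adoption are also a stated secondary objective, and section 12.4 plans GEE models of implementation outcomes such as prescriptions given.

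The exit questionnaire is the one delivery measure that the schedule collects from caregivers generally, in both arms and at every visit. Limiting its use in Arm B to a fifth of each provider's patients gives up information on the question that the Arm B monitoring is meant to answer. If the 20% was instead meant as a limit on collection, sections 6.4, 7.2 and 8.1.3 give staff conflicting instructions.

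**Working it through.** The plan states no figure for contamination precision, so there is none to reproduce. The check compares the section 6.4 rule with full use of A3.

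**Inputs from section 4:** 512 dyads, 33 to 34 providers (33.5 used) and 9 practices per arm. **From section 6.4:** 20%. **Assumed:** a true contamination rate p of 10%, and an ICC of 0, 0.04 or 0.1. The 0.04 is borrowed from section 12.2, where it refers to dental attendance within practices.

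**Questionnaires per visit, before attrition**
- Arm B total: 0.20 × 512 = 102.4, about 102, against 512.
- Per provider: 512/33.5 = 15.3, and 20% of that is 3.1.
- Per practice: 512/9 = 56.9, and 20% of that is 11.4.

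**Precision of the Arm B rate.** Half-width = 1.96 × √(p(1−p) × DEFF/n), with DEFF = 1 + (m−1) × ICC and m = n/9.
- ICC 0: n = 102 gives 1.96 × √(0.09/102) = 5.8 points; n = 512 gives 1.96 × √(0.09/512) = 2.6 points.
- ICC 0.04: DEFF = 1 + 10.33 × 0.04 = 1.41 and 1 + 55.89 × 0.04 = 3.24; half-widths 6.9 and 4.7 points.
- ICC 0.1: DEFF = 2.03 and 6.59; half-widths 8.3 and 6.7 points.

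The gain shrinks as clustering rises, but it remains. At other rates the half-widths (n = 102 against 512) are 4.2 against 1.9 points at p = 5% and 8.9 against 4.0 at p = 30% with ICC 0, or 5.0 against 3.4 and 10.6 against 7.1 with ICC 0.04.

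**If no contamination is seen.** The one-sided 95% upper bound is 1 − 0.05^(1/n): 2.9% for 0 of 102 and 0.6% for 0 of 512, ignoring clustering.

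**Within one provider at one visit.** When 3 of 15 families are sampled, the chance of finding at least one contaminated family is 1 − C(15−k, 3)/C(15, 3): 20%, 37%, 52% and 74% for k = 1, 2, 3 and 5.

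**Certification encounter, conditional.** Suppose it counts among the two to three observed at WCV #1 and is always a pass. A true pass rate r among the other encounters then appears as (1 + (j−1)r)/j, where j is the number observed. For an assumed r = 70% this is 85% (j = 2) or 80% (j = 3). For r from 50% to 90%, the inflation runs from +25 to +3 points. The text does not say that this encounter counts.

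**The case against.** The strongest reply is that a random 20% has the same expected value as a census, so only precision differs, and a half-width of 6 to 7 points is usable for a contamination check. The first part is correct. A reader might infer that the two arms cannot be fairly compared on delivery; the documents do not support that, because the Arm B questionnaires are randomly chosen, and the checklist and the number of observed encounters per provider match. The second part explains why the matter is modest. It gives no reason to set aside forms that the schedule already collects.

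The single-visit, single-provider detection figures also understate the plan. Take 20% at each of three visits with no attrition, independence and 10% contamination: 9 questionnaires find at least one case with probability 1 − 0.9^9 = 61%, and adding 3 observed encounters gives 1 − 0.9^12 = 72%. At practice level, 11 questionnaires at one visit give 1 − 0.9^11 = 69%. The plan promises no provider-by-provider detection, so the finding rests on the arm-level precision.

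A reader might further infer that Arm A fidelity is overstated because an assessed encounter close to training is scored. Section 6.3.1 lists that observation as part of training, section 6.3.2 treats monitoring separately, and nothing places it among the two to three. Encounters are observed or taped in both arms, so awareness of assessment is not peculiar to Arm A. Appendix B may contain the Arm A selection rule.

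Finally, section 6.4 could be read as limiting only the use of A3 for contamination, not its collection. That reading removes the contradiction but leaves the loss of precision.

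**Conclusion.** The point holds as a matter of efficiency and consistency, not bias. The section 6.4 rule yields about a fifth of the Arm B exit questionnaires that sections 7.2 and 8.1.3 would supply. At 10% contamination this widens the 95% interval by a factor of 2.2 without clustering (5.8/2.6) and 1.5 at an ICC of 0.04 (6.9/4.7). These figures assume one A3 per enrolled dyad at a visit, equal practice sizes and no attrition; the contamination rate and the ICC are assumptions.

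The missing Arm A selection rule is a secondary clarification, and any inflation of Arm A fidelity is conditional on the certification encounter being counted. The effect is confined to implementation and contamination measures. The primary analysis in section 12.4 includes participants regardless of compliance and does not use these samples.

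**What to change.** 1. Reconcile section 6.4 with sections 7.2.1 to 7.2.3 and 8.1.3, stating that A3 is collected from caregivers in both arms at all three visits.
2. In section 6.4, use all completed A3 questionnaires in both arms to estimate delivery and contamination, with intervals that allow for clustering.
3. In section 6.3.2, state random selection of the two to three encounters for Arm A as for Arm B, and report the section 6.3.1 certification encounter separately from the fidelity score. Align Appendix B if needed.

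The cost is mostly wording and a little more analysis. If Arm B collection was really meant to be 20%, there would also be additional short self-administered forms. If the certification encounter had been counted, one further observation per Arm A provider would be needed. Where visits are already complete, items 1 and 2 can still be applied to whatever A3 forms were collected, and certification encounters can still be reported separately if they are identifiable.
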